6.3 Exclusion Criteria

Patients are ineligible for the study if any of the following criteria are met:

1. Use of systemic corticosteroids within 6 weeks prior to Screening (or 5 half-lives, whichever is longer) or scheduled to receive systemic corticosteroids
2. Chronic use of antibiotic therapy within 3 months prior to Screening
3. Receipt of short-term antibiotic therapy within 14 days prior to Screening or use of antibiotics during the Screening period

4. Acute infection that requires antibiotic, antiviral, or antifungal therapy within 30 days prior to Screening
5. Nasal surgery (including polypectomy) within 6 months prior to Screening
6. Significant mechanical nasal airway obstruction due to septal deviation based on Investigator assessment
7. Use of investigational drugs or participation in another clinical trial within 30 days or 5 half-lives, whichever is longer, prior to Screening
8. Use of any medications that may interfere with the study, such as immunosuppressive drugs during the 2 weeks before Screening, or expected to require such medications through Day 168
9. Receipt of any live attenuated vaccines within 30 days or 5 half-lives, whichever is longer, prior to initiation of treatment in the study or expected to receive such a vaccine during the treatment period
10. Pregnancy or lactation in women
11. In patients with comorbid asthma, either of the following:
 - a) A FEV1 \leq 60% at Screening
 - b) An asthma exacerbation requiring systemic (oral and/or parenteral) steroid treatment or hospitalization for >24 hours for treatment of asthma within 30 days prior to Screening
12. History of human immunodeficiency virus (HIV) infection or other severe immunosuppressive disease, or positive HIV test at Screening
13. Current diagnosis or prior history of allergic fungal sinusitis, cystic fibrosis, ciliary dyskinesia, Wegener's Granulomatosis, or Churg-Strauss syndrome
14. Current diagnosis or prior history of any other condition likely to present with non-eosinophilic nasal polyps
15. History of hepatitis or active/chronic liver disease of any genesis or positive serology for hepatitis B virus (HBV) surface antigen or hepatitis C virus (HCV) antibody at Screening
16. Current diagnosis or history of cancer
17. A helminthic parasitic infestation, even if treated, within 6 months prior to Screening
18. History of or suspected history of cytokine release syndrome
19. Any disease or condition (medical or surgical) which, in the opinion of the Investigator, might compromise the hematologic, cardiovascular, pulmonary, renal, endocrine, autoimmune, gastrointestinal, hepatic, skeletal, or central nervous system; other conditions that might interfere with the absorption, distribution, metabolism or excretion of AK001 or would place the patient at increased risk (including any condition, such as diabetes, that would make it unsafe for the patient to fast as required by the study)

20. Known hypersensitivity to any constituent of the product

21. Legally institutionalized

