	
hematologic, cardiovascular, pulmonary, renal, endocrine, autoimmune, gastrointestinal, hepatic, skeletal, or central nervous systems; other conditions that might interfere with the absorption, distribution, metabolism or excretion of AK001 or would place the patient at increased risk (including any condition, such as diabetes, that would make it unsafe for the patient to fast as required by the study)
 
20. Known hypersensitivity to any constituent of the product
 
21. Legally institutionalized

TEST PRODUCT, DOSE, AND ROUTE OF ADMINISTRATION	AK001 25 mg or 250 mg, to be administered intravenously (IV) over approximately 1 hour on Days 0, 21, and 49
CONTROL PRODUCT, DOSE AND ROUTE OF ADMINISTRATION	Placebo, to be administered IV over approximately 1 hour on Days 0, 21, and 49
DURATION OF PATIENT PARTICIPATION AND DURATION OF STUDY	
Patients will participate in the study for up to approximately 32 weeks as follows:
 
 • Screening period: up to 4 weeks • Run-in period: 4 weeks • Treatment period: 7 weeks • Observation (Post-treatment period): 17 weeks

SAFETY EVALUATIONS
	
The safety and tolerability of 2 different dose levels of AK001 will be assessed by determining the incidence, relationship to study drug, and severity of TEAEs, withdrawals due to AEs, and changes in vital signs, laboratory test (including anti-drug antibody [ADA]) findings, concomitant medication use, and physical examination (PE) findings. Safety results in patients dosed with 2 different dose levels of AK001 will be compared with those in patients dosed with placebo (INS alone).
 
Each patient will remain at the Investigator site for a safety observation period of at least 8 hours following the end of each infusion. At the discretion of the Investigator, a longer monitoring period, if needed, may be implemented before the patient is discharged. Follow-up telephone calls will be made to the patient at 12 and 24 hours following the end of each infusion. Patients will be informed that, from discharge to the 24 hour telephone contact, they must be accompanied by another adult at all times, not travel alone or travel during bad weather, remain close to the location of the site, and have access to a telephone and transportation.

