2 RATIONALE FOR STUDY AND DOSE SELECTION

The present study is a Phase 2, randomized, double-blind, placebo-controlled study of the safety and tolerability of 2 different dose levels of AK001 compared with placebo in patients with moderate to severe chronic nasal polyposis and whose symptoms are resistant to treatment with INs.

In Study AK001-001, dose-related pharmacokinetic (PK) parameters, including maximum plasma concentration (C_{max}), area under the plasma concentration-time curve from zero hours to time (t) ($AUC_{[0-t]}$), and area under the plasma concentration-time curve from zero hours to infinity ($AUC_{[inf]}$), increased in a dose-proportional manner. The geometric mean (gMean) terminal elimination half-life ($t_{1/2}$) was in the range of 20 to 27 days, which is typical for a MAb. The gMean clearance ranged from 4.85 to 6.86 mL/hour and did not appear to be a function of body weight or body mass index (BMI). The gMean volume of distribution (V_z) was 0.060 L/kg, also typical for a MAb.

Siglec-8 internalization was durable and persisted as long as AK001 was present in serum. Siglec-8 internalization was not observed at Day 28 in the lowest dose cohort, 0.01 mg/kg, consistent with the undetectable levels of serum AK001 at Day 28. In all other dose cohorts, Siglec-8 internalization was maintained through Day 28.

The recommended Phase 2 doses of 25 mg and 250 mg administered IV every 3 to 4 weeks were calculated on the basis of nonclinical PK and pharmacodynamic data and on the PK and safety data collected in the Phase 1 study. These doses are expected to maintain 60% to 80% engagement and internalization of the Siglec-8 receptor; 60% to 80% internalization of the Siglec-8 receptor is associated with substantial inhibition of MCs and killing of activated eosinophils in in vitro experiments.

For additional information, please see the Investigator's Brochure (IB).

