6.2 Inclusion Criteria

Patients are eligible for the study if all of the following criteria are met:

1. Written informed consent
2. Male and female patients aged ≥ 18 and ≤ 75 years at the time of Screening
3. SNOT-22 (Appendix 5 [Section 19.5](#)) ≥ 30
4. At Screening, TPS of ≥ 5 for both nostrils with presence on endoscopy of nasal polyps of grade ≥ 2 in each nostril according to the polyp grading scale (Appendix 2 [Section 19.2](#))
Polyp grading scale for each nostril:
0=no nasal polyps
1=small polyps in the middle meatus not reaching below the inferior border of the middle turbinate
2=polyps reaching below the lower border of the middle turbinate
3=large polyps reaching the lower border of the inferior turbinate or polyps medial to the middle turbinate
4=large polyps causing complete obstruction of the inferior nasal cavity
5. History of at least 2 of the following symptoms for 4 weeks prior to Screening:
 - a) Anterior nasal discharge
 - b) Posterior nasal discharge
 - c) Nasal congestion, blockade, or obstruction

- d) Decreased sense of smell
- e) Facial pain or pressure
- 6. Received continuous topical nasal steroids and/or leukotriene receptor antagonists for at least 8 weeks prior to Screening unless failure or no effect of prior nasal steroid or leukotriene receptor antagonist therapy is documented
- 7. At randomization, received $\geq 80\%$ of doses of NASONEX scheduled during the Run-in period
- 8. At randomization, TPS of ≥ 5 for both nostrils with presence on endoscopy of nasal polyps of grade ≥ 2 in each nostril according to the polyp grading scale (see Inclusion Criterion #4 and Appendix 2 [Section 19.2](#)) and despite prior INS treatment during the Run-in period
- 9. Female patients must be post-menopausal for ≥ 1 year with documented follicle-stimulating hormone (FSH) > 30 IU/L, surgically sterile (tubal ligation, hysterectomy, or bilateral oophorectomy) for at least 3 months, or, if of child-bearing potential, willing to use a highly effective method of contraception (Appendix 1 [Section 19.1](#)) from Screening until at least 17 weeks after the last dose of the study drug is administered, which corresponds to approximately 5 half-lives of AK001

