7 PRIOR AND CONCURRENT MEDICATIONS

Prior and concomitant medications include both prescribed and over-the-counter medications. The Investigator is to record the use of all prior medications started within the 30 days before Screening and of all concomitant medications during the study in the Electronic Case Report Form (eCRF). Continuous topical nasal steroids and/or leukotriene receptor antagonists are to have been received for at least 8 weeks prior to Screening (Inclusion Criterion #6).

No medications as specified in Exclusion Criteria #1, #2, #3, #4, #7, #8, #9, and #11b are to have been received. On Day 0 before randomization, investigational site personnel should ensure that patients meet none of the exclusion criteria pertaining to medications. Patients should be advised against taking any new medication, both prescribed and over the counter, without consulting the Investigator, unless the new medication is required for emergency use.

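### Exclusion 9 looks ahead for a planned live attenuated vaccine only over the 7-week treatment period, although exposure peaks at the Day 49 infusion and Exclusion 8 looks ahead to Day 168

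*Protocol*

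**What the plan says.** Exclusion 9 has the same wording in the synopsis and in Section 6.3. Besides recent live vaccination, it excludes a patient "expected to receive such a vaccine during the treatment period". The synopsis entry on duration of participation defines the term: "Treatment period: 7 weeks", listed separately from a 17-week post-treatment observation period. Table 1 makes the same split: the treatment columns end at Day 50, and Days 84, 112 and 168 are post-treatment. Infusions are on Days 0, 21 and 49.

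Other parts of the protocol look further ahead:

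- Exclusion 8, on medications that may interfere with the study, covers patients "expected to require such medications through Day 168".
- Inclusion Criteria 9 and 10 require contraception until at least "17 weeks after the last dose of the study drug is administered, which corresponds to approximately 5 half-lives of AK001".
- Section 2 reports that the half-life "was in the range of 20 to 27 days, which is typical for a MAb" and that "Siglec-8 internalization was durable and persisted as long as AK001 was present in serum".

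Section 7 touches on vaccines only indirectly. It refers to Exclusion 9 by number ("No medications as specified in Exclusion Criteria #1, #2, #3, #4, #7, #8, #9, and #11b are to have been received") and gives general advice: "Patients should be advised against taking any new medication, both prescribed and over the counter, without consulting the Investigator", with an exception for emergencies. Section 7.1 does not list live vaccines as prohibited.

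**The concern.** Exclusion 9 is a question about plans, answered before randomization. Applied as written, it follows the dosing calendar and not the time the drug is present. A patient who says that a live attenuated vaccine is booked for the week after the third infusion is eligible under it, although drug levels within an active arm would then be close to their highest. The sponsor chose to screen for planned live vaccines, but the screen stops where modelled exposure peaks, and the protocol gives no reason for stopping there.

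What is at stake is a small matter of patient safety and of consistent screening across sites. The primary comparison, sample size and error control are not involved.

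**Working it through.** **Inputs.** Doses on Days 0, 21 and 49 (synopsis; Section 4.1). Treatment period 7 weeks and post-treatment period 17 weeks (synopsis). Half-life *t* = 20 to 27 days and dose-proportional pharmacokinetics (Section 2). Contraception window 17 weeks after the last dose, about 5 half-lives (Section 6.2). Exclusion 8 runs through Day 168 (Section 6.3).

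**The protocol's own window.** 49 + 17 × 7 = Day 168. Five half-lives in 119 days implies 119/5 = 23.8 days, inside the stated range. At the ends of that range the window is 119/20 = 5.95 and 119/27 = 4.41 half-lives, so the description as approximately 5 is reproduced.

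**Days not covered.** 168 − 49 = 119 days; 119/168 = 70.8%.

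**Exposure.** Assumptions: one compartment, first-order decay, each infusion treated as instantaneous, equal doses. Let f(d) = 2^(−d/t), with the first-dose peak set to 1.

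| Quantity | Formula | t = 20 | t = 27 |
|---|---|---|---|
| Peak after dose 2 | 1 + f(21) | 1.483 | 1.583 |
| Peak after dose 3, P3 | 1 + f(28) + f(49) | 1.562 | 1.772 |
| Share of P3 left, Day 56 | f(7) | 79% | 84% |
| Share of P3 left, Day 84 | f(35) | 29.7% | 40.7% |
| Share of P3 left, Day 112 | f(63) | 11.3% | 19.8% |
| Share of P3 left, Day 168 | f(119) | 1.6% | 4.7% |

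The share of AUC from Day 0 to Day 168 that falls after Day 49 is P3 × (1 − f(119)) / (3 − P3 × f(119)):

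- t = 20: 1.537/2.975 = 51.7%
- t = 27: 1.688/2.917 = 57.9%

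**Comparison between arms.** With a tenfold dose ratio, the 250 mg arm falls to the 25 mg arm's Day 49 peak at 49 + t × log2(10), which is Day 115.4 (t = 20) or Day 138.7 (t = 27). The percentages above are therefore within-arm figures. Placebo patients have no exposure.

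**Whether another rule closes the gap.**

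- Section 7 cites Exclusion 9 by number and so carries over the same 7-week window.
- The advice to consult the Investigator before a new medication is not an eligibility rule and gives no instruction about vaccines.
- Section 12.2 allows discontinuation when an exclusion criterion occurs, but at the Investigator's or Sponsor's discretion. It relies on Exclusion 9, which says nothing about the time after the treatment period.
- Exclusion 8 could be read broadly enough to catch such a patient. It does not name vaccines, and a separate vaccine criterion with its own shorter window points the other way.

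None of these extends the window.

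**The case against.** The strongest reply is that nothing here is misstated. Exclusion 9 reads the same in both places, and the treatment period is defined consistently. The longer windows serve other purposes: one is for contraception, the other for interfering medications. The protocol describes Siglec-8 as restricted to mature eosinophils, mast cells and, at lower levels, basophils. It does not call AK001 broadly immunosuppressive and gives no reason for Exclusion 9. AUC shares measure drug and not vaccine risk, and the number of patients planning a live vaccine between Day 50 and Day 168 is unknown and could be zero. All of this stands, and it limits the severity. It does not explain why a screen the sponsor chose to include should end at the last infusion of a drug with a half-life of 20 to 27 days.

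A second reply is that Day 168 is not the end of effect either. On the same model, the 250 mg arm retains 250 × 1.562 × 0.016 ≈ 6 mg to 250 × 1.772 × 0.047 ≈ 21 mg at Day 168. At an assumed 70 kg that is about 0.09 to 0.30 mg/kg. In Phase 1, every cohort above 0.01 mg/kg kept internalization through Day 28. This is fair: Day 168 is the protocol's own convention and the end of follow-up, not a proven end of pharmacological effect. It still covers nearly all of the modelled exposure.

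A third reply is that the change affects only an enrolment question and would not stop a vaccination arranged later. That is also true. The general advice in Section 7 remains the only safeguard there.

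**Conclusion.** The concern holds, at low severity. Followed exactly, Exclusion 9 admits a patient who already plans a live attenuated vaccine days after the third infusion. It leaves 119 of 168 days (71%) unscreened, and within each active arm 52% to 58% of modelled exposure over Days 0 to 168 falls in that stretch. The modelled level just after the Day 49 infusion is 1.56 to 1.77 times the first-dose peak.

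The day counts come directly from the protocol. The exposure figures rest on one-compartment decay, instantaneous infusions and the stated half-life range. They describe drug present and do not measure harm. The protocol states no vaccine-specific risk and gives no count of patients who would be affected. Efficacy, power and alpha are untouched.

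**What to change.** In Exclusion 9, in both the synopsis and Section 6.3, replace the reference to the treatment period with: through Day 168 (17 weeks after the last dose). This matches Exclusion 8 and the contraception window.

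Do not add live vaccines to Section 7.1. Section 12.2 discontinues participation for use of a drug prohibited there, so a patient vaccinated before Day 84 could be lost to the Week 12 assessment. With Exclusion 9 alone changed, a vaccination during follow-up could be treated as the occurrence of an exclusion criterion, but discontinuation would remain a matter for the Investigator and/or Sponsor.

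The change is one phrase in two places. Its cost is that an occasional patient defers a vaccine or is not enrolled.

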7 PRIOR AND CONCURRENT MEDICATIONS

Prior and concomitant medications include both prescribed and over-the-counter medications. The Investigator is to record the use of all prior medications started within the 30 days before Screening and of all concomitant medications during the study in the Electronic Case Report Form (eCRF). Continuous topical nasal steroids and/or leukotriene receptor antagonists are to have been received for at least 8 weeks prior to Screening (Inclusion Criterion #6).

No medications as specified in Exclusion Criteria #1, #2, #3, #4, #7, #8, #9, and #11b are to have been received. On Day 0 before randomization, investigational site personnel should ensure that patients meet none of the exclusion criteria pertaining to medications. Patients should be advised against taking any new medication, both prescribed and over the counter, without consulting the Investigator, unless the new medication is required for emergency use.

7.1 Prohibited Medications

All medications taken during the conduct of this study must be documented on the eCRF. The use of immunosuppressive drugs is prohibited during the 2 weeks before Screening and systemic corticosteroids is prohibited during the 6 weeks before Screening (or 5 half-lives, whichever is longer) and during the study, except as necessary to treat AEs under the direction of the Investigator.

7.2 Allowed Medications

Medications (other than those that are prohibited [[Section 7.1](#)]), such as asthma medications, are allowed during the study and, unless dose changes are required due to unforeseen medical necessities, doses are to remain stable. All medication use will be documented in the eCRF.

If a patient experiences an infusion-related reaction that is considered mild to moderate (e.g., itching or a localized rash), an antihistamine, acetaminophen, and, if needed, a glucocorticoid (e.g., IV methylprednisolone 125 mg) may be administered. If a patient experiences signs or symptoms of anaphylaxis, the patient will be treated with standard-of-care medications, such as diphenhydramine, acetaminophen, methylprednisolone, epinephrine, and other supportive measures along with cessation of the infusion.

8 STUDY TREATMENTS

8.1 Method of Assigning Patients to Treatment Groups

Each patient who provides informed consent will be assigned a Screening number that uniquely identifies him or her.

Approximately 70 patients who complete the Screening and Run-in periods of the study will be randomized in a double-blind fashion to receive 1 of the following treatments:

- Arm A: AK001 25 mg (n=25)
- Arm B: AK001 250 mg (n=25)
- Arm C: Matching placebo (n=20)

The randomization will be stratified by the presence of comorbid asthma. Enrollment will be staggered; no more than 1 patient will be randomized every 4 weeks at each site.

Randomization will occur on Day 0 via interactive voice or web response system (IXRS) after confirmation that the patient meets all inclusion and no exclusion criteria. An unblinded non-study statistician will produce the randomization schedule with a fixed reproducible random seed for use in the IXRS.

8.2 Intranasal Steroid Adjustment

After the patient has completed the Screening procedures, the patient will enter a 4-week Run-in period to achieve a stable regimen with a common intranasal topical steroid (NASONEX [mometasone furoate monohydrate]) and discontinue any other intranasal topical steroids. The Day -28 visit may occur as soon as the day after Screening. Patients will be instructed to self-administer 2 NASONEX nasal inhalations in each nostril twice a day from the start of the Run-in period through the end of the study. The patient will record the date and time of each dose taken in a dosing diary. Inclusion and exclusion criteria may continue to be assessed while the patient is in the Run-in period.

Patients must have received $\geq 80\%$ of doses of NASONEX scheduled for the Run-in period to be randomized.

8.3 Blinding

The identity of test and control treatments will not be known to Investigators, research staff, patients, or the study monitor. Members of the DMC can request the identity of treatments if needed. The following study procedures will be in place to ensure double-blind administration of study treatments:

- Access to the randomization codes will be strictly controlled via IXRS
- Throughout the study, the blind should remain unbroken except and only for an emergency when knowledge of the patient's study medication is necessary for further patient management or if required for regulatory reporting. When possible, the Investigator should discuss the emergency with the Medical Monitor prior to unblinding.
- The prepared test and control IV infusion solutions will be identical in appearance

Other than under the conditions described above, the study blind will be broken on completion of the study after the study database has been locked.

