1 BACKGROUND

Nasal polyps are benign edematous masses that can cause nasal obstruction, rhinorrhea, facial pressure, postnasal drip, and loss of smell. It is estimated that nasal polyps affect 1% to 4% of the general population with a 2:1 male to female preponderance. The incidence increases with age, with peak incidence between 40 and 60 years of age.^{1,2} Although the etiology of nasal polyposis (recurrent, multiple polyps)² is unknown, various comorbidities, such as chronic inflammation of the mucous membranes in the nose and paranasal sinuses, allergic rhinitis, atopy, and asthma, have been proposed as factors in the genesis of nasal polyposis.^{3,4}

Phenotypically, chronic rhinosinusitis (CRS) can be classified as either without nasal polyposis (CRSsNP) or with nasal polyposis (CRSwNP), which comprises the majority of cases of nasal polyposis. The more common CRSwNP is characterized by eosinophilic inflammation with high levels of eosinophil cationic protein; interleukin (IL)-4, IL-5, and IL-13; and tissue immunoglobulin E (IgE).^{2,5}

Treatment options for nasal polyposis range from topical and/or systemic corticosteroids to functional endoscopic sinus surgery.⁵ Patients with CRSwNP and comorbid asthma, in particular, have a poor therapeutic response and high recurrence rate, and their diseases are more difficult to treat. Both diseases have an adverse effect on quality of life and confer a large economic burden.³

AK001 is a humanized immunoglobulin G4 (IgG4) monoclonal antibody (MAb) directed against Siglec-8, a member of the CD33-related family of sialic acid-binding, immunoglobulin-like lectins (siglecs). No close homolog has been found in other animal or primate species apart from great apes and baboons. Consequently, AK001 has been studied in Siglec-8 humanized and transgenic mouse models and with human blood and tissue cells. Siglec-8 has a restricted tissue distribution and is expressed selectively on the surface of mature eosinophils, mast cells (MCs), and at lower levels on basophils but not in early precursors of these cell populations or other blood cells. Crosslinking of Siglec-8 by AK001 can induce apoptosis of eosinophils previously activated by certain cytokines. The antibody does not induce apoptosis in MCs, but inhibits histamine release and de novo synthesis of prostaglandin D2 (PGD2) induced by IgE-receptor activation.

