5.3 Efficacy Endpoints

The following specific efficacy endpoints will be evaluated:

- TPS (Appendix 2 [Section 19.2](#)) by blinded centralized evaluation of endoscopy
- Size of polyps as evaluated by Lund-Mackay score (Appendix 3 [Section 19.3](#)) at selected Investigator sites by CT scan
- Nasal airway patency as evaluated by PNIF
- UPSIT (Appendix 4 [Section 19.4](#))
- SNOT-22 (patient-reported symptoms) (Appendix 5 [Section 19.5](#))
- VASs (patient-reported symptoms) (Appendix 6 [Section 19.6](#))
- Clinical symptoms improvement scale³ (Appendix 6 [Section 19.6](#))
- SF-36 (quality of life) (Appendix 7 [Section 19.7](#))
- Blood eosinophil and basophil absolute counts

The following specific additional efficacy endpoints will be evaluated in patients with comorbid asthma:

- TPS (Appendix 2 [Section 19.2](#)) by blinded centralized evaluation of endoscopy
- Pulmonary function (FEV1, FVC, and FEF) assessed using spirometry

- ACT (Appendix 8 [Section 19.8](#))
- Use of asthma rescue therapy

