9.3 Clinical Safety Laboratory Measurements

Blood and urine samples will be obtained for clinical safety laboratory tests (hematology, chemistries, and urinalyses) and for ADA as specified in [Table 1](#) and [Sections 9.3.2, 9.3.3, and 9.3.5](#). Blood for clinical safety laboratory tests will be collected following an overnight fast (8 hours) from food and beverages other than water. The duration of the fast should be no longer than the typical overnight sleeping period for the patient.

Certified laboratories will be used to process and provide results for the clinical safety laboratory tests. The Baseline laboratory test result will be defined as the last measurement prior to the first infusion of study drug.

For any laboratory test value outside the reference range that the Investigator considers clinically significant, the Investigator will:

- Repeat the test to verify the out-of-range value
- Follow the out-of-range value to a satisfactory clinical resolution

The Investigator will record as an AE any laboratory test value that (1) is confirmed and the Investigator considers clinically significant, (2) that requires a patient to be discontinued from the study, or (3) that requires a patient to receive treatment.

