9.3.2 Hematology

Blood will be obtained at Screening; on Day -3; pre-dose on Days 21 and 49, and on Days 14, 84, 112, and 168 or ET for a complete blood count (CBC) with differential: hemoglobin, hematocrit, red blood cell count, white blood cell (WBC) count, WBC differential, and platelet count.

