9.6 Efficacy Measurements

Specific information on the collection, processing storage, and shipment of samples will be provided in a separate manual.

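### Does Investigator access to eosinophil and basophil counts in the safety differential break the blind?

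*Protocol*

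**What the plan says.** Section 8.3 sets the blind: "The identity of test and control treatments will not be known to Investigators, research staff, patients, or the study monitor". It lists three measures: control of the randomization codes, unblinding only for emergencies or regulatory reporting, and infusions that look alike. None concerns laboratory results.

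Section 5.3 lists "Blood eosinophil and basophil absolute counts" among the efficacy endpoints. Neither Table 1 nor Section 9.6 schedules a separate draw for them. Section 9.3.2 takes blood at Screening, on Day -3 and on Days 14, 21, 49, 84, 112 and "168 or ET for a complete blood count (CBC) with differential". Of the tests scheduled, only this one gives the counts.

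Hematology is a safety laboratory test under Section 9.3: "Certified laboratories will be used to process and provide results for the clinical safety laboratory tests". The Investigator then has duties: "For any laboratory test value outside the reference range that the Investigator considers clinically significant, the Investigator will" repeat the test and follow the value to a satisfactory resolution. Section 9.6 refers sample handling to a manual that was not available: "Specific information on the collection, processing storage, and shipment of samples will be provided in a separate manual".

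On mechanism, Section 1 says "Crosslinking of Siglec-8 by AK001 can induce apoptosis of eosinophils previously activated by certain cytokines". Section 2 links the chosen doses to receptor internalization associated with "killing of activated eosinophils in in vitro experiments".

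**The concern.** A pharmacodynamic marker that blinded staff can read is a familiar way for a double-blind trial to leak. If AK001 lowered blood eosinophils visibly, a site could compare counts before and after dosing and form a view of the arm. Nothing in Section 8.3 would stop it, and by naming the counts as efficacy endpoints the sponsor shows that an effect on them is worth looking for.

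What depends on site judgment is not trivial: peak nasal inspiratory flow, measured at the site (Section 9.6.6); the Investigator's view of adverse event causality, which feeds the stopping rules in Section 14.3; concomitant treatment; and withdrawal at the Investigator's discretion (Section 12.2). Patient-reported scores would be touched only if the suspicion reached the patient.

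**Working it through.** **1. Is there a contradiction?** Section 8.3 protects the identity of the treatment. Sections 9.3 and 9.3.2 give the Investigator laboratory values. A value reveals identity only if it separates the arms, so the passages conflict only if a recognisable fall occurs.

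**2. Does the protocol give evidence of such a fall?**

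| Point | Where | What it supports |
|---|---|---|
| Apoptosis of eosinophils already activated by certain cytokines | Section 1 | An effect on activated cells; nothing on total circulating count |
| Killing of activated eosinophils | Section 2 | In vitro only |
| Basophils express Siglec-8 at lower levels | Section 1 | Expression; no depletion is claimed |
| No clinically relevant hematology change | Section 1.2 | Clinical evidence against a marked fall |
| Internalization kept through Day 28 in all cohorts but the lowest | Section 2 | The Phase 1 result was obtained with the target engaged |

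The exposure was comparable in amount. Body weight is not given; assuming 60-80 kg, the Phase 1 top single dose is 10 mg/kg x 60 to 80 kg = 600 to 800 mg, against 3 x 250 = 750 mg over the high-dose course here.

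**3. What would a fall do if it happened?** The protocol gives no size of fall and no within-patient variation, so everything below is a scenario. Assumptions: log-normal counts, independent within-patient variation with a CV of 30-50%, a constant fall after dosing, and a guesser who uses the best possible cut-off.

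- Share on active: p = 50/70 = 0.714, so always guessing active is right for 71.4%. L = ln(p/(1-p)) = 0.916.
- s² = ln(1 + CV²) = 0.2231 at CV 50% and 0.0862 at CV 30%.
- With a pre-dose and b post-dose counts averaged on the log scale, SD = sqrt(s² x (1/a + 1/b)).
- Same fall in both arms: D = -ln(1 - fall)/SD; accuracy = p·Φ(D/2 + L/D) + (1 - p)·Φ(D/2 - L/D).
- Unequal falls: accuracy = ∫ max{[25·f25 + 25·f250]/70, 20·fplacebo/70}, with normal densities centred at ln(1 - fall) for each arm.

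Worked case, 50% fall in both arms, CV 50%. One pair of counts: SD = sqrt(0.2231 x 2) = 0.668, D = 0.693/0.668 = 1.038, accuracy 75.9%. A site eventually has two pre-dose counts (Screening, Day -3) and six post-dose counts: SD = sqrt(0.2231 x (1/2 + 1/6)) = 0.386, D = 1.797, accuracy 84.4%.

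| Assumed fall, 25 mg / 250 mg | One pre, one post (CV 50% to 30%) | Two pre, six post (CV 50% to 30%) |
|---|---|---|
| 20% / 20% | 71.4-71.9% | 72.0-74.8% |
| 30% / 30% | 71.8-74.1% | 74.7-81.0% |
| 50% / 50% | 75.9-83.0% | 84.4-93.5% |
| 25% / 50% | 72.5-75.8% | 76.5-82.4% |
| 0% / 50% | 71.4% | 71.4% |

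The last row follows because the 25 mg arm then behaves like placebo but is larger (25 against 20), so active is always the better guess. Individual patients can still stand out. With a true 50% fall at 250 mg only, and one pair of counts, half of that arm and 15.0% (CV 50%) or 4.7% (CV 30%) of the others show a halving. The probability of AK001 given a halving is (25 x 0.5 + 25 x 0.150)/(25 x 0.5 + 45 x 0.150) = 84.4%, or 93.5% with 0.047 (fractions rounded for display).

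The right-hand column overstates what a site knows when it acts. All six post-dose counts exist only at Day 168; by the Day 84 flow measurement there are at most four. An average site has 70/14 = 5 patients, 20/14 = 1.4 of them on placebo, from which to learn a cut-off.

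**4. What does the primary analysis rest on?** Sections 9.6.3 and 9.6.4 have endoscopy videos scored centrally by an independent blinded reviewer, so scoring of the primary endpoint does not depend on the site's belief.

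**The case for a change.** The strongest case for the concern is that every citation in it is right. The counts are endpoints, the safety differential is their only scheduled source, the Investigator reads it, and no section masks it. Release of results is a matter of trial conduct and is not normally left to an SAP, and the manual named in Section 9.6 is described as covering sample handling only. Phase 1 does not settle the matter: it gave single doses to 26 people, healthy volunteers or atopic patients, whereas this trial gives three doses in a presumably eosinophilic disease. The absence of a clinically relevant change also does not exclude a fall within the normal range. If both arms did fall, the scenarios show that sites could guess materially better than chance, already from about 30% when several counts are combined.

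All of that stands as a possibility. It does not make the plan wrong, and the remedy is not free. To mask the two counts, enough of the rest of the differential must be withheld that they cannot be found by subtraction. Section 9.3 requires the Investigator to act on abnormal values, Section 12.2 counts eosinophilia among the findings the Investigator weighs, and Section 14.1 has the sponsor's Medical Monitor review safety data as they arrive. Releasing values on request helps little, since nobody asks about an abnormality they cannot see. A periodically convened monitoring committee is not a routine reader, and supplying one would mean a further unblinded role.

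**Conclusion.** The concern does not hold as a finding. The gap in Section 8.3 is real, but it contradicts no other statement and causes no demonstrated loss of blinding. The chain needs a visible fall in circulating counts, then a site's suspicion, then altered conduct. The document shows none of these, and its only clinical evidence points against the first.

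No size can be given from the document. Under assumed falls the gain over 71.4% runs from nothing (250 mg arm only) through at most 3.4 percentage points (20% in both arms, all counts: 74.8 - 71.4) to about 22 points (50% in both arms, CV 30%, all counts: 93.5 - 71.4 = 22.1). Every one of these figures rests on an assumed fall and an assumed CV.

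Whether to mask part of a safety differential in a trial that describes itself as one of safety and tolerability is a trade-off on which reasonable statisticians and safety physicians differ. The sponsor's choice to leave it visible is defensible. The judgment would change if data on AK001 showed a clear fall in blood eosinophils at these doses; the protocol reports none.
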